4.3.8 US of hip(s)

Information on hip(s) US will be collected for patients based on availability in the patient charts. If US done at screening, information on US is not be required at baseline.

Information on hip(s) US will be collected for patients based on availability in the patient charts at 6, 12 months to evaluate changes of inflammation parameters.

The following parameters of active inflammation will be determined:

- Joint effusion (expressed as Yes or No)
- Distance between lower margin of femoral neck and lower part of joint capsule expressed in millimeters
- Enthesitis at sites where ligaments and tendons are attached to bone in structures adjacent to the hip joint (expressed as Yes or No)
- Change of enthesitis from previous examination (Positive change or No change or Negative change)

At the moment, there is no standardized US scores available for hips. This is the reason for collecting information on each individual US sign of inflammation and for placing change of US signs in the Exploratory objectives.

Product: MK-8259

Protocol/Amendment No.: 021

VEAP ID NO: 6189

Date: 15-January-2018

4.3.9 Concomitant medications

Data will be captured on medication given for the treatment of AS. These medications include: NSAIDs, disease-modifying antirheumatic drugs (DMARDs) (e.g. Sulfasalazine and methotrexate), corticosteroids, medications for comorbidities and medications for other extra-articular manifestations. For medications, the categories of medications will be recorded.

4.3.10 Comorbidities

Information on comorbidities, which is part of routine medical assessment of AS patients, will be collected at baseline. They will include:

- Inflammatory bowel disease
- Uveitis
- Psoriasis
- Hypertension
- Stroke
- Ischemic heart disease (angina pectoris and/or myocardial infarction)
- Lung Disease
- Asthma
- Chronic obstructive pulmonary disease
- Pulmonary fibrosis
- Renal disease
- Liver disease
- Peptic ulcer disease
- Thyroid disease
- Depression
- Cerebrovascular accident
- Demyelinating disease
- Epilepsy
- Diabetes
- Tuberculosis
- Malignancy
- Mental illness other than depression
- Gastrointestinal disease
- Anemia or other blood disorder

Product: MK-8259

Protocol/Amendment No.: 021

VEAP ID NO: 6189

Date: 15-January-2018

- Fibromyalgia

- Other

4.4 Laboratory Variables

4.4.1 HLA-B27 Genotyping

HLA-genotype will be recorded as HLA-B27 positive or negative. The information will be obtained from the patients' medical records and no additional genetic testing will be required as part of the study.

Product: MK-8259

Protocol/Amendment No.: 021

VEAP ID NO: 6189

Date: 15-January-2018

5 Study Flow Chart

Study period	Screening	Observation				
		Visit 2 Baseline	Visit 3	Visit 4	Visit 5	Visit 6
Visit Number/ Title	Visit 1 Screening					
Study Day/Month	Days -28 thru 0	Day 1	Month 6	Month 12	Month 18	Month 24
Scheduling Window	-	-	+6 weeks	+6 weeks	+6 weeks	+6 weeks
Informed Consent	X ^a	X ^a				
Subject Identification Card		X				
Inclusion/Exclusion Criteria	X	X				
Age	X	X				
Gender		X				
Weight		X				
Occupational status		X	X	X	X	X
AS diagnosis duration		X				
Radiographic stage of sacroiliitis		X				
Coxitis symptoms duration		X				
Golimumab administration registration		X	X	X	X	X
BASFI		X	X	X	X	X
BASMI		X	X	X	X	X
ASDAS-CRP		X	X	X	X	X
BASDAI		X	X	X	X	X
BASRI-hip	X	X ^c		X		X
MRI signs	X ^b	X ^c	X	X		
US signs	X ^b	X ^c	X	X		
CRP		X	X	X	X	X
HLA-B27		X				
Comorbidities	X	X				
Concomitant Medications		X	X	X	X	X
Adverse Events		X	X	X	X	X

a - Informed consents form is provided after the treating physician has made the decision to prescribe golimumab but before the patient receives the treatment

b – Coxitis can be confirmed with MRI and/or US at Screening

c – If Hip X-rays and MRI/US done at screening, information on Hip X-ray and MRI/US is not required at baseline

Product: MK-8259

Protocol/Amendment No.: 021

VEAP ID NO: 6189

Date: 15-January-2018

6 STUDY PROCEDURES

The Study Diagram in Section 5 summarizes the study procedures to be performed at each visit. Individual study procedures are described in detail below. It may be necessary to perform these procedures at unscheduled time points if deemed clinically necessary by the investigator. Furthermore, additional evaluations/testing may be deemed necessary by the Sponsor for reasons related to subject safety.

6.1 Study Procedures

The Study Diagram in Section 5 summarizes the study procedures to be performed at each visit. Individual study procedures are described in detail below.

6.1.1. Administrative procedures

6.1.1.1 General Informed Consent

Consent must be documented by the subject's dated signature or by the subject's legally acceptable representative's dated signature on a consent form along with the dated signature of the person conducting the consent discussion.

A copy of the signed and dated consent form should be given to the subject before participation in the study.

The initial informed consent form, any subsequent revised written informed consent form and any written information provided to the subject must receive the IRB/ERC's approval/favorable opinion in advance of use. The subject or his/her legally acceptable representative should be informed in a timely manner if new information becomes available that may be relevant to the subject's willingness to continue participation in the study. The communication of this information will be provided and documented via a revised consent form or addendum to the original consent form that captures the subject's dated signature or by the subject's legally acceptable representative's dated signature.

Specifics about a study and the study population will be added to the consent form template at the protocol level.

The informed consent will adhere to IRB/ERC requirements, applicable laws and regulations and Sponsor requirements.

6.1.2. Other Procedures

6.1.2.1. Withdrawal/Discontinuation

The patient may withdraw his/her consent to participate in the study at any time for any reason. This decision will not have any consequences for his/her future medical care.

The investigator may exclude a patient from the study at any time if he/she finds that continuation of participation in the study might be harmful or does not meet interests of the patient: for safety, lack of efficacy or any other reason.

The sponsor may stop the study at any time. In such case, all investigators will be informed in advance.

Product: MK-8259
Protocol/Amendment No.: 021
VEAP ID NO: 6189
Date: 15-January-2018

6.1.2.2 Data Collection

Data will be collected from multiple centers. Based on the protocol, a CRF will be developed for data collection. Each local center will be asked to enter the data into the CRFs. All the data entered in the CRF will be entered into a single database stored centrally and analyzed.

6.1.2.3 Interim Statistical Analysis

Interim Statistical Analysis will be performed when at least 18 patients recruited are observed and have their tests done at 12 months.

6.1.2.4 Central collection and evaluation of X-ray, MR Images and US protocols

Radiographs, MR images and US protocols will be collected and analyzed centrally in the Rheumatology Research Institute after being evaluated by the radiologists and rheumatologists of the investigational sites.

Central collection and evaluation will be performed when at least 18 patients recruited are observed and have their tests done at 12 and 24 months.

Central collection of images will not interfere with daily clinical practice as it will take place after local evaluation.

6.1.3 Clinical Procedures/Assessments

6.1.3.1. Collection of Demographic data.

The demographic parameters including age, gender, weight, employment status will be recorded at baseline.

6.1.3.2. Duration of AS diagnosis and coxitis symptoms.

Time from AS diagnosis and from the beginning coxitis symptoms will be recorded at baseline.

6.1.3.3. Radiographic stage of sacroiliitis

Radiological stage of sacroiliitis (I, II, III, IV) will be recorded at baseline.

6.1.3.4. Golimumab administration registration.

Data on golimumab usage as well as reasons for discontinuation of treatment will be collected at baseline and at 6, 12, 18, 24 months.

Reasons for discontinuation are withdrawal of the informed consent form by the patient for any reason, decision of the investigator to stop administration of golimumab due to safety concerns and/or due to lack of efficacy.

6.1.3.5. BASFI

Level of BASFI (Bath AS Functionality Index) at baseline and at 6, 12, 18, 24 months.

6.1.3.6. BASMI

Level of BASMI (Bath AS Metrological Index) will be recorded at baseline and at 6, 12, 18, 24 months.

6.1.3.7. ASDAS-CRP

Level of ASDAS-CRP will be recorded at baseline and at 6, 12, 18, 24 months.

Product: MK-8259

Protocol/Amendment No.: 021

VEAP ID NO: 6189

Date: 15-January-2018

6.1.3.8. BASDAI

Level of BASDAI will be recorded at baseline and at 6, 12, 18, 24 months.

6.1.3.9. BASRI-hip

BASRI-hip score determined based on hip(s) conventional X-ray will be recorded at screening as one of the inclusion criterion, at baseline and at 12, 24 months.

6.1.3.10. Hip(s) MRI

Information on hip(s) MRI (STIR (short tau inversion recovery) sequence and fat-saturated contrast-enhanced T1-weighted sequence) will be recorded at screening as one of the inclusion criterion (confirmation of coxitis) or at baseline and at 12 months.

6.1.3.11. Hip(s) US

Information on hip(s) US will be recorded at screening as one of the inclusion criterion (confirmation of coxitis) or at baseline and at 6, 12 months.

6.1.3.12. Concomitant medications

Information on medication (name and category) given for the treatment of AS will be recorded at baseline and at 6, 12, 18, 24 months.

6.1.3.13. Comorbidities

Information on comorbidities, which is part of routine medical assessment of AS patients, will be recorded at baseline.

6.1.4 Laboratory Procedures/Assessments

6.1.4.1. HLA-B27 Genotyping

HLA-genotype will be recorded as HLA-B27 positive or negative at baseline. This information will be obtained from the patients' medical records.

6.1.4.2. C-reactive protein.

Level of CRP will be recorded in mg/l at baseline and at 6, 12, 18, 24 months.

7 Safety Reporting and Related Procedures

Introduction

This is a primary data collection non-interventional study being conducted within routine medical practice. All direction for medication usage is at the discretion of a physician in accordance with usual medical practice. No administration of any therapeutic or prophylactic agent is required in this protocol, and there are no procedures required as part of this protocol.

7.1 Adverse Event Reporting

7.1.1 INVESTIGATOR RESPONSIBILITY:

If the investigator becomes aware of any serious adverse event (SAE), including death due to any cause, or non-serious adverse reaction (NSAR) following the use of Simponi®, or any other MSD product, the

Product: MK-8259
 Protocol/Amendment No.: 021
 VEAP ID NO: 6189
 Date: 15-January-2018

event must be reported according to Table 1. The investigator must evaluate each SAE for causality and record causality on the AE form for each event reported.

Similarly, pre-specified Health Outcomes of Interest (HOIs) that meet criteria for SAE/NSAR, special situations, and any spontaneously reported AEs must be reported according to Table 1.

Table 1: AE Reporting Timeframes and Process for Investigators

EVENT TYPE	INVESTIGATOR TIME FRAME
	Investigator to MSD [1], [2]

 • SAE, regardless of causality • Serious pre-specified Health Outcome of Interest (HOI) • Serious Special Situation, regardless of causality 	24 hours from receipt

 • Non-serious Adverse Reaction (NSAR) • Non-Serious pre-specified HOI if NSAR • Non-serious Special Situation, regardless of causality 	10 calendar days from receipt

 • Spontaneously reported adverse events for MSD products-submit using above timeframes • If the investigator elects to submit AEs for non-MSD products, they should be reported to the market authorization holder (MAH) for that product or to the health authority according to the institution's policy or local laws and regulations 	
Follow-up to any event-submit using above timeframes	

[1] AE reports from investigators must be transmitted via fax, secure email (if available), or entered directly into vendor's electronic data collection (EDC) platform, if utilized.
 
[2] Investigator to Merck: Applies to studies that do not have a vendor managing AEs.
	

Submitting AE reports to Merck Global Safety: All AEs must be submitted to the local MSD Russia Office via [contact] and email [contact], in English using an AE form ([attached](#)) for reporting to worldwide regulatory agencies as appropriate. Then, from the local MSD Russia Office, the AE form is to be submitted to the PAEL Mailbox within 1 business day.

Enhanced Malignancy Reporting

All malignancies occurring in patients 30 years of age or younger who received Golimumab must be reported to sponsor or designee within 24 hours using the same method described in the protocol for SAE reporting.

In addition, there will be follow-up from the Sponsor or designee (CRO) to the Investigator using a dedicated Malignancy Follow-up Questionnaire that needs to be completed by the Investigator and submitted to the Sponsor or designee within 2 weeks of receipt, using the same method described above for SAE reporting. The Investigator must make at least 2 attempts to contact the patient or guardian to complete the Malignancy Follow-up Questionnaire. If the attempts are not successful, the reason for

Product: MK-8259

Protocol/Amendment No.: 021

VEAP ID NO: 6189

Date: 15-January-2018

each unsuccessful attempt must be documented (e.g., patient lost-to-follow-up, patient refuses to supply the additional information, etc.).

The Sponsor or designee (CRO) will review the study AE database for possible premalignant conditions twice a year. If any are reported, the Sponsor or designee will contact the Investigator with a dedicated follow-up request that needs to be completed. In case a pre-malignant condition has progressed to a malignancy, the Investigator will need to complete the Malignancy Follow-Up Questionnaire.

7.1.2 STUDY REPORT

The final study report, and any planned interim analysis, will include aggregate listings of all events collected for Simponi® and will be provided to regulatory agencies by the sponsor as required.

7.1.3 PERIODIC SAFETY UPDATE REPORTS

Any relevant safety information will be summarized in the appropriate Periodic Safety Update Report (PSUR)/Periodic Benefit Risk Evaluation Report (PBRER) and/or Development Safety Update Reports (DSUR) if required.

7.2 DEFINITIONS

7.2.1 Adverse Event (AE)

Any untoward medical occurrence in a patient or clinical investigation subject administered sponsor's product and which does not necessarily have to have a causal relationship with this product. An adverse event can therefore be any unfavorable and unintended sign (including an abnormal laboratory finding, for example), symptom, or disease temporally associated with the use of the product, whether or not considered related to the product. Any worsening (i.e., any clinically significant adverse change in frequency and/or intensity) of a preexisting condition that is temporally associated with the use of the product, is also an adverse event.

7.2.2 Adverse Reaction (AR); also referred to as Adverse Drug Reaction (ADR)

An AE which has a causal relationship with the product, that is, a causal relationship between the product and the adverse event is at least a reasonable possibility.

7.2.3 Serious Adverse Event (SAE)/Serious Adverse Reaction (SAR)

An adverse event or adverse reaction that results in death, is life threatening, results in persistent or significant disability/incapacity, requires inpatient hospitalization, prolongation of existing inpatient hospitalization, is a congenital anomaly/birth defect, or is another important medical event. Other important medical events that may not result in death, may not be life-threatening, or may not require hospitalization may be considered an SAE/SAR when, based upon appropriate medical judgment, they may jeopardize the patient or subject and may require medical or surgical intervention to prevent one of the other outcomes listed previously. Examples of such medical events include allergic bronchospasm requiring intensive treatment in an emergency room or at home and blood dyscrasias or convulsions that do not result in inpatient hospitalization.

7.2.4 Non-serious Adverse Reaction (NSAR)

An adverse reaction that does not meet any of the serious criteria in 7.2.3.

Product: MK-8259
Protocol/Amendment No.: 021
VEAP ID NO: 6189
Date: 15-January-2018

7.2.5 Special Situations

The following special situations are considered important safety information and must be reported, regardless of seriousness or causality, if the investigator becomes aware of them:

- Overdose
- Exposure to product during pregnancy or lactation
- Lack of therapeutic effect
- Off-label use, medication error, misuse, abuse, or occupational exposure
- Suspected transmission via a medicinal product of an infectious agent

7.2.6 Health Outcome of Interest (HOI)

Health Outcomes of Interest (HOIs) are pre-specified clinical events or outcomes that are collected according to the protocol. HOIs may be represented as diagnosis, treatment or procedures. Examples of HOIs include syncope or hypoglycaemia collected as study endpoints. HOIs must be assessed as part of AE collection and may meet criteria for AE reporting. Specifically, the investigator must assess each HOI for serious criteria and causality. If the HOI meets criteria specified in the protocol for AE reporting, then it must be reported as such.

7.2.7 Sponsor's product

Sponsor's product includes any pharmaceutical product, biological product, device, diagnostic agent or protocol-specified procedure, whether investigational (including placebo or active comparator product) or marketed, manufactured by, licensed by, provided by or distributed by the Sponsor for human use.

7.2.8 Causality Assessment

A causality assessment is the determination of whether or not there is at least a reasonable possibility that a product caused the adverse event. Causality must be recorded on the AE form by the investigator for each reported event in relationship to a Sponsor's product.

Primary Data Collection

The assessment of causality is to be determined by an investigator who is a qualified healthcare professional according to his/her best clinical judgment. Use the following criteria as guidance (not all criteria must be present to be indicative of causality to a Sponsor's product): There is evidence of exposure to the Sponsor's product; the temporal sequence of the AE onset relative to the administration of the Sponsor's product is reasonable; the AE is more likely explained by the Sponsor's product than by another cause.

8 Statistical Analysis Plan

8.1 Statistical Methods

Quantitative variables will be tested for normal distribution using the Shapiro-Wilk test. The hypothesis of equality of variances will be tested using Levene's test. Quantitative variables matching a normal distribution will be described in terms of the mean \pm standard deviation, and values outside of the normal distribution as medians, 25% and 75% quartiles. Qualitative variables will be presented in the form of percentages of the absolute value N.

Product: MK-8259

Protocol/Amendment No.: 021

VEAP ID NO: 6189

Date: 15-January-2018

Quantitative variables that meet normal distribution criteria and equality of variances will be compared using Student's paired t-criteria. The Wilcoxon signed rank will be used to compare quantitative variables that do not meet normal distribution or equality of variance criteria.

Comparative analysis of qualitative variables will use a Chi-square test. If at least one of the absolute rates is less than 5, an exact two-sided Fischer's test is to be used.

Descriptive analysis will be used for the following:

- 1) description of the study population at the baseline;
- 2) data completeness;
- 3) distributions of reasons for discontinuation for the study population;
- 4) attrition of the study population;
- 5) durability and variability of responses.

Descriptive analysis is to be done via completion of standard tables and creation of graphical representation of each patient over time as his/her own line connecting each data point.

8.1.1 Interim Statistical Analysis

Interim Statistical Analysis will be performed when at least 18 patients recruited are observed and have their tests done at 12 months.

8.1.2 Primary Objective: Calculation of Epidemiological Measure of Interest

- Change of BASFI score from baseline to 12 months of therapy

8.1.3 Secondary Objectives: Calculation of Epidemiological Measures of Interest

- Change of BASFI score from baseline to 24 months of therapy
- Change of BASMI score from baseline to 12 and 24 months of therapy
- Change of ASDAS-CRP score from baseline to 12 and 24 months of therapy
- Change of BASDAI score from baseline to 12 and 24 months of therapy
- Change of BASRI-hip score from baseline to 12 and 24 months of therapy

8.1.4 Exploratory Objectives: Calculation of Epidemiological Measures of Interest

- Change of MRI signs from baseline to 6 and 12 months of therapy (will be presented descriptively)
- Change of US signs from baseline to 6 and 12 months of therapy (will be presented descriptively)
- Mean clinical scores (BASFI, BASMI, ASDAS-CRP, BASDAI) in subgroups of patients with or without MRI/US signs at baseline and their change at 12 months
- Change of employment status of patients at 12 and 24 months of therapy (will be presented descriptively)

Product: MK-8259
Protocol/Amendment No.: 021
VEAP ID NO: 6189
Date: 15-January-2018

8.2 Bias

8.2.1 Methods to Minimize Bias

Potential sources of bias are errors in recruitment, early drop out of patients from the study, deviation of administration of golimumab from the label of Simponi®.

Bias from errors in recruitment of patients can be reduced with rigorous adherence to inclusion/exclusion criteria when recruiting patients for the study.

Bias from early drop out of patients from the study can be reduced with Interim Statistical Analysis which is to be performed when at least 18 patients recruited are observed and have their tests done at 12 months. Also, patients who drop out before final follow up visit are planned to enter an analysis of last-observation-carried forward (LOCF). Data recorded on the last visits of patients will contribute to the analysis.

Deviation from the label of Simponi® are determined as delays of injections for more than 2 weeks at least 2 times per year. Data from patients with such delays are to be analyzed separately.

8.2.2 Limitations

In this non-interventional study the quality of the data is important. Therefore, it is important for the sponsor or designee to monitor data completion and perform quality checks during the course of the study. To minimize missing data, a set of core variables is required to be available at enrollment as part of inclusion criteria.

This study will collect data on patients being treated in real clinical Rheumatology practice. It is expected that the number of patients dropping out before completion of the whole course of observation will be about 30%. To minimize this limitation, the study will enroll 39 patients to ensure that the number of subjects entering the analysis *Per Protocol* will be enough (27 subjects). In addition, secondary analyses will evaluate data on completers vs patients dropping out before completion separately.

The potential issue of missing data is limitation of the study. To minimize this limitation, patients with missing data are planned to enter the analysis of LOCF. Data recorded on the last visits of patients or the visit after the missing one will contribute to the analysis.

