2.3 Exploratory objectives

- To evaluate change of MRI signs of coxitis in AS from baseline to 12 months of therapy with golimumab in daily clinical practice
- To evaluate change of US signs of coxitis in AS from baseline to 12 months of therapy with golimumab
- To evaluate mean clinical scores (BASFI, BASMI, ASDAS-CRP, BASDAI) in subgroups of patients with or without MRI/US signs at baseline and their change at 12 months
- To evaluate occupational status of AS patients with coxitis at 12 and 24 months of therapy with golimumab in daily clinical practice

Data collected at 12 and 24 months are to be used for statistical analysis. But if these data is unavailable (e.g. due to early drop out before the final follow-up) data collected at 6 and 18 months are to be used according to analysis of last-observation-carried forward (LOCF) to minimize bias – section 8.2.1.

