3 METHODOLOGY

3.1 Summary of Study Design

This study is a non-interventional prospective observational cohort study. Patients participating after signing informed consent form will receive treatment and diagnostic procedures according to daily clinical practice conducted by his/her physician.

Visits during the study will include collection of data if already available. There are no procedures that are required as part of this study.

The study is to be conducted in multiple centers across Russia. AS patients with coxitis newly prescribed golimumab during the course of usual clinical care, will be enrolled and followed prospectively for 24 months with data collection at the approximate time points: baseline (pre-treatment) and consequent every 6 months. A time window of approximately \pm 6 weeks is envisaged for follow-up visits.

Product: MK-8259

Protocol/Amendment No.: 021

VEAP ID NO: 6189

Date: 15-January-2018

Patients will be screened and selected according to inclusion and exclusion criteria prior to enrollment. The study centers will maintain a list of all screened patients with the reasons for excluding patients being enrolled into the study.

Baseline data will be extracted from medical records (MR), if available at each treatment center. No additional interventional tests or medical procedures such as additional blood samples, X-ray or other technical investigations will be performed as a part of this study. If any data element is not available it will be reported as missing.

At baseline, data on age, gender, occupational status, AS and coxitis symptoms duration, concomitant disease, will be collected according to usual clinical practice.

C-reactive protein (CRP) is usually measured as part of the normal screening for patients prior to the initiation of a biologic agent in clinical practice. The results of this measurements will be collected. No additional blood withdrawals will be necessary for the study. CRP will be collected at baseline and at 6, 12, 18, 24 months if the measurements are available in regular clinical practice. Human leukocyte antigen B27 (HLA-B27) status (i.e. positive or negative) will be collected at baseline if available. Most AS patients will have this test performed as part of the diagnostic work-up in clinical practice.

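### Section 8.2.2 labels as LOCF a rule that also allows the next visit, with no order of preference; if LOCF reaches BASRI-hip, drop-outs are scored as unchanged since their last film

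*Combined protocol and SAP*

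**What the plan says.** Three sections give a missing-data rule.

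- Section 2.3, closing paragraph: if month-12 or month-24 data are unavailable, "data collected at 6 and 18 months are to be used according to analysis of last-observation-carried forward (LOCF) to minimize bias". It refers to section 8.2.1.
- Section 8.2.1: patients who leave early enter an LOCF analysis that uses their last visit.
- Section 8.2.2: patients with missing data enter the LOCF analysis, and "Data recorded on the last visits of patients or the visit after the missing one will contribute to the analysis". No order of preference is given and no endpoint is excluded.

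Section 8.2.2 also plans that "secondary analyses will evaluate data on completers vs patients dropping out before completion separately".

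The primary measure (8.1.2) is "Change of BASFI score from baseline to 12 months of therapy". BASFI is scheduled at baseline, 6, 12, 18 and 24 months. A secondary measure (8.1.3) is "Change of BASRI-hip score from baseline to 12 and 24 months of therapy". Hip films are scheduled at baseline (or screening), 12 and 24 months only (3.1, 4.3.6, section 5), and depend on what is in the chart. Section 1.2 expects BASRI-hip to stay unchanged at 12 and 24 months.

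**The concern.** Two things follow from the wording.

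First, a value taken from a later visit is not a last observation carried forward. For a patient seen at months 6 and 18 but not at month 12, section 8.2.2 permits either BASFI score, while section 8.2.1 looks back. Section 2.3 names months 6 and 18 under the LOCF label. The primary mean can thus be computed in more than one way from the same data, and the choice could be made after the data are seen.

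Second, the month 6 and 18 substitutes do not exist for BASRI-hip. If LOCF is applied to it, a patient lost after the month-12 film keeps the month-12 grade at month 24. If baseline may be carried, a patient lost before month 12 is scored as exactly zero change at both time points. The imputation would then supply part of the result that the study expects to find, and carried grades would make the estimate look more precise than the films allow.

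**Working it through.** **Inputs.** From sections 8.2.2 and 8.3: 39 enrolled, about 30% loss over 24 months (range 21-37%), 27 completers, planning BASFI change -2.5 with SD 2.12. Assumed: a constant loss rate, loss unrelated to outcome, month-6 BASFI equal to month 12, and BASRI-hip grades that do not improve. The documents give no progression rate.

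**The plan's own figure.** 39 × 0.70 = 27.3, which agrees with 27 completers and leaves about 12 drop-outs (39 × 0.21 = 8 to 39 × 0.37 = 14).

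**Retention,** for 24-month loss L = 0.21 / 0.30 / 0.37:
- S24 = 1 - L = 0.79 / 0.70 / 0.63
- S12 = (1 - L)^0.5 = 0.889 / 0.837 / 0.794
- Lost before month 6 = 1 - (1 - L)^0.25 = 0.057 / 0.085 / 0.109

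**BASFI, last or next visit.** One patient's value enters the mean with weight 1/39 = 0.026, so the mean moves 0.026 points per affected patient per 1-point difference between months 6 and 18. Only intermittent gaps are affected, because a drop-out has no later visit.

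**BASFI, if baseline were carried.** Shift = 2.5 × share lost before month 6 = 0.14 / 0.21 / 0.27. At 30% loss that is 39 × 0.085 = 3.3 patients, and a mean of -2.29 instead of -2.50.

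**Significance.** With 37% of patients scored as no change, the mean is 2.5 × 0.63 = 1.575 and the SD is √(0.63 × (2.12² + 2.5²) - 1.575²) = 2.07. With n = 39, a two-sided 5% paired t-test has power 99.6%.

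**BASRI-hip.** Let p be the share of 24-month progression already present at month 12 (0 to 1).
- Baseline films carried: reported/true at month 24 = S24 + p(S12 - S24).
- Baseline films not carried: the denominator is patients with a month-12 film, and reported/true = S24/S12 + p(1 - S24/S12).

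| Under-count | 21% loss | 30% loss | 37% loss |
|---|---|---|---|
| Month 24, baseline carried | 11-21% | 16-30% | 21-37% |
| Month 24, baseline not carried | 0-11% | 0-16% | 0-21% |
| Month 12, baseline carried | 11% | 16% | 21% |
| Month 12, baseline not carried | 0% | 0% | 0% |

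At 30% loss, month-24 grades carried are 39 × (1 - 0.70) = 11.7, about 12 of 39, if baseline is allowed. If it is not, they are 39 × (0.837 - 0.70) = 5.3, about 5 of 39 × 0.837 = 33. As an illustration, an assumed true 20% worsening would be reported as 14.0-16.7% with baseline carried and 16.7-20.0% without.

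**Apparent precision with no progression.** The exact upper 95% bound is 1 - 0.025^(1/n): 9.0% for 0/39, 10.6% for 0/33, and 12.8% for 0/27, the films actually seen.

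**Which statistic is affected.** These factors apply to a mean change or a proportion worsening. Section 8.1 describes non-normal variables by medians and quartiles, and "The Wilcoxon signed rank will be used to compare quantitative variables that do not meet normal distribution or equality of variance criteria". One-grade changes in a minority of patients are far from normal. With 20% worsening, the median change is 0 with or without carrying. If zeros are dropped, as is usual, carried zeros leave the signed-rank p-value unchanged: five worsenings give 2 × (1/2)^5 = 0.0625 whether n is 27 or 39.

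**The case against.** The strongest defence is that the proven defect is narrow. Sections 2.3 and 8.2.1 already look back, and next-visit fill can arise only for an intermittent gap. The planned comparison of completers with drop-outs will show some of the effect. That stands as a limit on size. It does not choose between two permitted values, and it does not remove carried grades.

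A reader might infer several stronger points that the documents do not support.

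- *The plan biases BASFI by about 0.2 points.* That needs baseline to be carried, which no section states; section 2.3 names only months 6 and 18. Under random loss with month 6 equal to month 12, LOCF without baseline carry returns the planning change.
- *The primary test is at risk.* It is not, at the planning effect.
- *About 12 of 39 BASRI-hip grades will be carried and progression under-counted by up to 30%.* That is only the less favourable reading; without baseline carry it is about 5 grades and 0-16%.
- *The bias always favours stability.* Filling a missed month-12 film from month 24 would err the other way if damage progresses. If true progression is near nil, as in two studies described in section 1.1, bias in the estimate is small and only precision is overstated.
- *Section 3.1 offers an observed-only analysis as an equal alternative*, because "If any data element is not available it will be reported as missing". In context this is a data-recording rule, compatible with later imputation.

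Whether BASFI scores recorded after golimumab is stopped count toward the endpoint is also unstated, but that is a separate question.

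**Conclusion.** The concern holds in a limited form. The text of 8.2.2 contradicts its own label and the other two sections, and leaves two permitted month-12 BASFI values for some patients. The numerical effect on the primary mean is small.

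The BASRI-hip point is conditional on LOCF being applied to that endpoint, which the plan neither states nor excludes. If it is, drop-outs are held at their last grade, in the direction the study expects. The size depends on constant loss unrelated to progression, on grades not improving, and on whether baseline may be carried, so both rows of the table should be read together. A median or Wilcoxon result under 8.1 would change little; a mean change, a proportion worsening or a statement about stability would be affected. The matter should be fixed before analysis, but it does not threaten the primary conclusion.

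**What to change.** **Wording (the minimum).** Delete the next-visit option from 8.2.2. State one look-back rule, in the same words, in 2.3, 8.2.1 and 8.2.2. Say whether baseline may be carried and to which endpoints the rule applies.

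**BASRI-hip.** Use no carry-forward. Report the change among patients with a film at that visit. Add the number worsening by at least one grade with an exact 95% CI, and base any statement of stability on the upper bound.

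**BASFI, BASMI, ASDAS-CRP and BASDAI.** Preferably, estimate the month-12 change with its 95% CI from a repeated-measures model on all observed visits, with visit as a factor. Keep as sensitivity analyses the paired t or Wilcoxon test with look-back LOCF, the completers analysis, and one in which drop-outs are returned to baseline.

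**Cost.** SAP text and a standard model on scores already planned, with no change to eligibility, visits or sample size. BASRI-hip has a smaller denominator and a wider interval: 0/27 gives an upper bound of 12.8%, so a firm statement of stability may be out of reach. If drop-outs in truth return to baseline, the model overstates benefit: -2.50 against -2.5 × 0.837 = -2.09 at 30% loss, a gap of 0.41 (0.28-0.52 over 21-37%). That exceeds the shift from carrying baseline, so the return-to-baseline result must be shown beside the model.
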